5.2 Subject Exclusion Criteria

All subjects meeting any of these listed exclusion criteria at baseline will be excluded from study participation:

- 1. Significant liver dysfunction as evidenced by at least 5 times greater than upper limits of normal baseline ALT, AST, alkaline phosphatase, or total bilirubin.
- 2. Use of an alternative antifungal therapy (IV or oral) for more than 14 days for this infection with the exception of Coccidioidomycosis. Subjects with Coccidioidomycosis who previously received fluconazole therapy for more than 14 days may be included, if in the opinion of the investigator, they are having an inadequate response or, are intolerant of fluconazole (e.g. due to adverse events). Such subjects must washout from fluconazole for 7 days (~5 half-lives of fluconazole) before starting investigational therapy.
- 3. Evidence of CNS infection.
- 4. Unable to take PO medications.
- 5. Female subjects who are lactating or pregnant.

- 6. Female subjects should be:
 - a) Postmenopausal for 1 year,
 - b) Post-hysterectomy or bilateral oophorectomy,
 - c) If of child bearing potential have a negative β-HCG at screening and using highly effective method of birth control throughout course of study or remain abstinent for duration of study.
- 7. Male subjects with female partner(s) of child-bearing potential, must agree to use a medically acceptable method of contraception during the study. If their partner is pregnant, males must agree to use a condom; if their partner is of child-bearing potential, their partner must additionally be using one of the following methods: hormonal contraception, intra-uterine device, diaphragm, or cervical cap. Spermicides alone are not an acceptable method of contraception. No sperm donations for 90 days post last dose of study therapy.
- 8. Documented intolerance, allergy or hypersensitivity to an azole.
- 9. Inability to comply with study treatment, study visits, and study procedures.
- 10. Known history of congestive cardiac failure on medical treatment, fungal endocarditis, or other causes of ventricular dysfunction that may outweigh the benefit of itraconazole.
- 11. Patients with active TB
- 12. Concurrent use of astemizole, rifampin/rifampicin, rifabutin, ergot alkaloids, long acting barbiturates, carbamazepine, pimozide, quinidine, neostigmine, terfenadine, ketoconazole, valproic acid, or St. John's wort in the 5 days prior to first administration of study drug.

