6.5 Concomitant Medications/Treatments

6.5.1 Collection

Concomitant medications will be collected from signing of informed consent all the way through to the end of study visit. Any medications taken within 2 weeks of Study Day 1, even if prior to ICF collection date, should be noted.

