6.5.2 Restricted Concomitant Medications

Itraconazole may affect the plasma concentration of other drugs, as it is an inhibitor of CYP3A4 as well as P-gp (P-glycoprotein). Sites should carefully evaluate concomitant medication use to ensure that possible drug interactions do not affect the health of the patient.

Drugs that may decrease plasma concentrations of itraconazole include:

| Category | Examples |
|--|---|
| Anticonvulsants | carbamazepine, phenobarbital, phenytoin |
| Antimycobacterials | isoniazid, rifabutin, rifampin |
| Non-Nucleoside Reverse Transcriptase Inhibitors | nevirapine |

GI Medications

Additionally, certain anti-acids, H2 blockers, and protein pump inhibitors are prohibited with conventional itraconazole. If possible, H2 blockers and protein pump inhibitors should be stopped 7 days prior to enrollment, at the discretion of the treating physician. Anti-acids may be taken 1-2 hours AFTER oral dosing with study drug.

Drugs that can increase plasma concentrations of itraconazole include:

| Category | Examples: |
|-----------------------|------------------------------|
| Macrolide Antibiotics | clarithromycin, erythromycin |
| Protease Inhibitors | indinavir, ritonavir |

Alternative fungal medications administered for more than 14 days prior to the first dose of study medication are prohibited unless subject with coccidioidomycosis previously treated with fluconazole therapy for more than 14 days. If in the opinion of the investigator, the subjects with coccidioidomycosis are having an inadequate response or, are intolerant of fluconazole (e.g.due to adverse events), the subjects may be included. Such subjects must washout from fluconazole for 7 days (~5 half-lives of fluconazole) before starting investigational therapy.

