7 STUDY SCHEDULE

7.1 Screening

Patients presenting to the clinic or hospital with new onset presumed or definite endemic fungal infection that have not been treated with an alternative antifungal medication for more than 14 days prior to study drug administration; and with no known exclusion criteria by medical history will be given informed consent to enroll in the study.

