10.3 Study Outcomes

Stage I- Randomized Open-Label, Parallel Group

Primary Endpoints

- 1. Pharmacokinetic superiority at Day 14
 - a) Inter- and intra- patient variability: Time to attain therapeutic plasma concentrations of itraconazole (> 500 mcg/L)
 - b) Interpatient variability as calculated by co-efficient of variation

Trough (pre-morning dose) sample will be collected at Days 14 and 42. Using validated LC-MS/MS methods, blood samples will be analyzed to quantify plasma concentrations of itraconazole and hydroxyitraconazole.

Participants should arrive to the trial site having **not** taken their morning dose of study drug.

Note: site investigators are discouraged from drawing independent PK laboratories to check itraconazole levels outside of the designated timepoints (Day 14)

2. Tolerability - ability to remain on study drug at Day 42 with less than a 7-day interruption of therapy

Secondary Endpoints

- PK at day 7 plasma concentrations of itraconazole- (comparative trough, steady state plasma itraconazole concentrations of SUBA-itraconazole 65mg capsules with food to itraconazole 100mg capsules with food over 7 days)
- 2. PK at day 42 plasma concentrations of itraconazole- (comparative trough, steady state plasma itraconazole concentrations of SUBA-itraconazole 65mg capsules with food to itraconazole 100mg capsules with food over 42 days)
- 3. Efficacy: clinical outcomes (time to relief of fungal signs and symptoms) at days 14, 28, and 42
- 4. Safety- defined as: adverse events that occurred in each study arm by Day 42
- 5. Tolerability ability to remain on study drug at Days 14 & 28
- 6. Days of Hospitalization and ICU stays at Day 42
- 7. Other health economic endpoints:
 - 1. Number of unscheduled procedures (i.e., labs, scans, etc.) at Day 42
 - 2. Total number of capsules taken at Day 42
 - 3. SF-20 (QOL) assessments at Day 42

Stage II- Open-Label, Extension

Primary Endpoint

- 1. Efficacy- Free from proven or probable invasive endemic fungal infection at Day 180
- 2. Tolerability- ability to stay on study drugs at Days 43 180.

Secondary Endpoints

- 1. Safety- Adverse events that occurred in each study arm between Days 43 180 or end of therapy
- 2. Days of Hospitalization (Days 1 180) defined as days of hospitalization and ICU stays from randomization to Day 180 or end of therapy)

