APPENDIX A: SCHEDULE OF EVENTS

| Activities | Day 1 ^g (Baseline) | Day 7 (1 wk) +/- 3 days | Day 14 (2 wks) +/- 3 days | Day 28 (4wks) +/- 7 days | Day 42 (6 wks) +/- 3 days | Day 84 (3 mos) +/- 7 days | Day 180 (6 mos) +/- 7 days |
|---|----------------------------------|----------------------------------|------------------------------------|-----------------------------------|------------------------------------|------------------------------------|-------------------------------------|
| Informed Consent | Х | | | | | | |
| Review of Inclusion/Exclusion Criteria | × | | | | | | |
| Randomization | X | | | | | | |
| Medical History | X | | | | | | |
| Clinical Assessment: vital signs, PE ^a , & radiographs ^b ; | × | Х | Х | Х | Х | Х | × |
| Participant Administered SF-12 Quality of Life Survey | Х | | | | Х | | х |
| Tolerability | Х | | | Х | Х | | Х |
| βHCG - pregnancy test ^c | Х | | | | | | |
| Mycologic Assessment: clinical, urine and serum quantitative antigen levels^d & serum antibodies ^{e,f} | х | | х | Х | Х | Х | х |
| Serum and Urine for future use: blood, urine, saliva, sputume | X | | Х | X | Х | Х | Х |
| Plasma PK ^f | | Χ | Х | | Х | | |
| Chemistry: Creatinine, AST and Alkaline Phosphatase, Total Bilirubin ^f | Х | | Х | Х | Х | Х | х |
| Hematology: CBC with Differential ^f | X | | | X | | X | X |
| HIV Status: Documentation of any positive test; Documentation of Negative test 30 days or less prior to start of study drug. | Х | | | | | | |
| Antifungal Therapy (Pre- and during study) | Х | Х | Х | Х | Х | Х | Х |
| Dose Modifications | | | Х | X | Х | Х | |
| Study Drug Dosing & Accountability | Х | Х | Х | Х | Х | Х | Х |
| Concomitant Therapy | Х | Х | Х | Х | Х | Х | Х |
| Adverse Events | Х | Х | Х | Х | Х | Х | Х |
| Days of Hospitalization, ICU | Х | Х | Х | Х | Х | Х | Х |

^a Complete physical exam on baseline; targeted physical exams for all other visits.

b Radiograph results that were performed as standard of care to diagnose or assess the fungal infection.

^C Urine or Serum pregnancy test is acceptable.

^d Histoplasma and Coccidioides urine and serum quantitative antigen.

^e Collection of sputum, if associated with the IFI and available.

^fChemistry and hematology will be processed at the site for safety evaluations; PK samples will be sent to a central lab for processing; see Manual of Procedures for specimen handling procedures;

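### Recent non-study itraconazole is neither excluded nor washed out and no level is drawn before Day 7, so for patients already above 500 mcg/L on Day 1, primary component 1(a) does not measure the assigned formulation

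*Combined protocol and SAP*

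**What the plan says.** **Eligibility.** Section 5.2, item 2 excludes "Use of an alternative antifungal therapy (IV or oral) for more than 14 days for this infection with the exception of Coccidioidomycosis". Section 6.5.2 repeats the limit ("Alternative fungal medications administered for more than 14 days prior to the first dose of study medication are prohibited"), and so does section 7.1 ("that have not been treated with an alternative antifungal medication for more than 14 days prior to study drug administration"). None of the three defines 'alternative' or names itraconazole. The one antifungal washout, also in item 2, concerns coccidioidomycosis patients coming off fluconazole: "Such subjects must washout from fluconazole for 7 days (~5 half-lives of fluconazole) before starting investigational therapy". Item 12 of section 5.2 lists ketoconazole among the drugs barred in the 5 days before first dose, but not itraconazole.

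**Endpoint.** The first primary endpoint of Stage I in section 10.3 is PK superiority at Day 14. Its component 1(a) is "Time to attain therapeutic plasma concentrations of itraconazole (> 500 mcg/L". No rule covers a patient who is above that level before the first study dose.

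**Sampling.** Section 10.3 says "Trough (pre-morning dose) sample will be collected at Days 14 and 42" and lists Day 7 PK as a secondary endpoint. Appendix A marks plasma PK at Days 7, 14 and 42 and leaves Day 1 blank. Section 10.3 also discourages sites from drawing their own itraconazole levels at other times.

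**What is recorded.** Appendix A has a row for "Antifungal Therapy (Pre- and during study", marked at Day 1 and at every later visit. Section 6.5.1 adds: "Any medications taken within 2 weeks of Study Day 1, even if prior to ICF collection date, should be noted".

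**Analysis.** Section 10.1 plans t-tests and chi-square tests. It moves to linear or logistic regression only if the arms turn out to differ on measured baseline characteristics. Section 5.3.1 stratifies randomization by HIV status alone.

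**The concern.** Both arms deliver the same molecule. A patient who arrives on non-study itraconazole may already be above 500 mcg/L, and the time to attain that level is then zero or undefined whichever capsule is assigned. Because no level is taken on Day 1, the trial cannot identify these patients by concentration. They will be counted as reaching the threshold by the first sample, exactly as a patient who absorbed the study drug quickly would be.

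Two things are at stake. First, carry-over in both arms pulls the early PK results together and can hide a real formulation difference. Second, if the arms happen to differ in the number pre-treated, the early comparison shifts for a reason unrelated to formulation. The contingent adjustment in section 10.1 can respond to the second problem but not to the first.

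**Working it through.** **1. Can such patients enter?** There are two readings of 'alternative'.

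- If it includes itraconazole, up to 14 days of prior itraconazole is compatible with entry.
- If it means antifungals other than itraconazole, the clause sets no limit on prior itraconazole.

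No other criterion closes the gap under either reading. Section 6.2 links non-study conventional itraconazole to standard care for these infections, so prior use is plausible. No document gives its frequency.

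**2. Can they be identified by level?** No. The Day 7 visit has a window of ±3 days, so the first level falls between Day 4 (7 − 3) and Day 10 (7 + 3). The observable outcomes for 1(a) are: above by the first sample, first above at Day 14, first above at Day 42, or never above. A patient above on Day 1 who stays above falls in the first group, together with those who reached the level on study drug.

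**3. The plan's own power figure.** The inputs from section 10.2 are a difference of 60.0, SDs of 94.0 and 101.8, N = 80 and two-sided alpha 0.05. Allocation is not stated, so I assume 40 per arm.

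- SE = √(94.0²/40 + 101.8²/40) = √(220.9 + 259.1) = 21.91
- Noncentrality = 60/21.91 = 2.74
- Welch power = 77.2%, so the stated 77% reproduces.

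This is power for a difference in means. It is not power for time to threshold, and section 10.2 does not tie it to Day 7.

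**4. How dilution works.** Let f be the share pre-treated, equal in both arms, and c the fraction of the formulation contrast that pre-treated patients still show at the time of measurement. The share of the true contrast kept is 1 − f(1 − c). Both f and c are assumptions, because the documents give neither.

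| f | c = 0 | c = 0.8 |
|---|---|---|
| 10% | 90% | 98% |
| 25% | 75% | 95% |
| 40% | 60% | 92% |

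A value of c near 0 is reasonable for 1(a) in a patient already above the threshold. A higher c is reasonable at Day 14, after about two weeks on the assigned drug, including the three-times-daily dosing on Days 1–3 (section 6.2). The arms are perfectly balanced in this calculation, so the section 10.1 trigger would not fire. A main-effect covariate would not restore the lost contrast either, because the adjusted estimate still averages over both kinds of patient.

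**5. Chance imbalance.** Take the numbers pre-treated as independent Binomial(40, f) in each arm. The probability of a difference of at least 4 patients (4/40 = 10 percentage points) is 19% for f = 10%, 33% for 20% and 39% for 30%.

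**6. Where does restriction pay?** Restricting to patients without prior itraconazole keeps the whole contrast but multiplies the SE by 1/√(1 − f). At equal SDs, it improves the signal-to-error ratio when √(1 − f) > 1 − f(1 − c), that is, when c < 1 − (1 − √(1 − f))/f.

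- f = 10%: 1 − 0.0513/0.10 = 0.49
- f = 25%: 1 − 0.1340/0.25 = 0.46
- f = 40%: 1 − 0.2254/0.40 = 0.44

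Restriction therefore helps when pre-treated patients keep less than roughly half of the contrast. That fits 1(a). It is not a reason to drop them from the Day 14 concentration comparison.

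**The case against.** The strongest opposing points are these.

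- **The number affected may be small.** Section 7.1 describes new-onset infection, and section 2.1 says that severe disease has traditionally been treated first with amphotericin B. Therapy before entry need not have been itraconazole. This stands, and it keeps the point minor.
- **Randomization balances prior use in expectation, and section 10.1 adjusts for observed differences.** This stands for imbalance, so a reader who infers that the plan has no adjustment goes too far. Prior antifungal therapy is recorded and could enter the section 10.1 models. However, that adjustment is contingent, does not name prior azole use, offers no time-to-event method and does not touch balanced dilution.
- **A covariate does not cure dilution, and restriction costs patients.** Both are true. Steps 4 and 6 show why the two parts of the fix have different purposes.
- **A coarser problem affects everyone.** With a first level at Day 7, time to threshold is interval-censored in all patients, and the present fix leaves that as it is.

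Two further inferences are tempting but unsupported. One is that the protocol expressly allows 14 days of itraconazole. It does not say so; the text is silent and the key word undefined. The other is that power falls from 77% to 68%, 53% or 37% if 10%, 25% or 40% are pre-treated. That arithmetic is correct for differences of 54, 45 and 36. But it applies a difference-in-means calculation to another quantity, assumes zero contrast in pre-treated patients (implausible by Day 14), and uses shares that appear nowhere in the documents.

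**Conclusion.** The point holds as a gap in the definition and analysis of early PK. Nothing bars or washes out recent itraconazole, no Day 1 level exists, and 1(a) has no rule for patients already above 500 mcg/L. Followed as written, the plan can credit non-study drug to the assigned formulation.

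Its size cannot be stated, because the share pre-treated is unknown. In direction, the effect is dilution. It should be largest for 1(a) and the Day 7 level and smaller for the Day 14 concentration. The ranges shown above are illustrations on assumed values of f and c with 40 per arm, and no loss should be set against the 77%. This is a cheap improvement and does not threaten the trial's validity.

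**What to change.** 1. State whether 'alternative' antifungal therapy in sections 5.2, 6.5.2 and 7.1 includes itraconazole.
2. Derive one baseline indicator, any itraconazole in the 14 days before Day 1, from the pre-study antifungal therapy and the two-week medication look-back already collected.
3. Pre-specify that indicator as a covariate in the Day 7 and Day 14 PK models, whether or not imbalance is seen. This gains precision and handles chance imbalance. It does not restore diluted contrast, and the text should not claim that it does.
4. Analyse time to exceed 500 mcg/L in patients without prior itraconazole, and report the all-patient analysis alongside. The restriction uses a baseline variable, so the comparison remains a randomized one.
5. Fix this wording before outcome data are examined, since the trial is open-label and a later choice would be open to question.

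The cost is analysis text and one derived variable, with no new sample, visit or eligibility change. The 1(a) set shrinks by the number pre-treated: for example, from 40 to 36, 30 or 24 per arm if 10%, 25% or 40% were pre-treated (40 × (1 − f), shares assumed).

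### Drugs that Section 6.5.2 says alter itraconazole levels may be on board at the primary Day 14 PK sample, and Section 10.1 does not plan for them

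*Combined protocol and SAP*

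**What the plan says.** Section 5.2 applies its criteria at one moment: patients meeting any of the "listed exclusion criteria at baseline will be excluded from study participation". Item 12 lists "Concurrent use of astemizole, rifampin/rifampicin, rifabutin, ergot alkaloids, long acting barbiturates, carbamazepine, pimozide, quinidine, neostigmine, terfenadine, ketoconazole, valproic acid" and St. John's wort, and closes with "wort in the 5 days prior to first administration of study drug". It has no clause for the treatment period.

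Section 6.5.2 names drugs that lower itraconazole levels: the anticonvulsants "carbamazepine, phenobarbital, phenytoin", the antimycobacterials "isoniazid, rifabutin, rifampin", and nevirapine. It names drugs that raise them: "clarithromycin, erythromycin" and "indinavir, ritonavir". For use during the trial its instruction is: "Sites should carefully evaluate concomitant medication use to ensure that possible drug interactions do not affect the health of the patient". A separate, stricter rule there covers acid-lowering drugs with conventional itraconazole; it is not the subject of this point.

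Plasma PK is scheduled at Days 7, 14 and 42 (Appendix A). Day 14 PK is a Stage I primary outcome (Section 3.2.1), and the between-patient coefficient of variation (CV) is part of that endpoint (Section 10.3). Section 10.1 plans a t-test, with regression adjustment only if the arms are seen to differ at baseline. Section 6.5.1 records concomitant drugs from consent to the final visit, and any taken in the 2 weeks before Day 1.

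**The concern.** By the protocol's own account, some permitted co-medication changes the quantity being measured. Seven drugs named in 6.5.2 are absent from exclusion 12. Even a drug on both lists, such as rifampin or carbamazepine, is not barred after the first dose. The instruction for that period protects the patient's health and does not address the PK measurement.

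A few depressed or raised levels widen the spread in each arm. That lowers the power of the Day 14 comparison, which starts at 77%, and inflates the CV, which is itself a primary measure. An uneven split of users between arms moves the estimated difference. Section 10.1 has no rule for any of this unless a baseline imbalance is noticed.

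**Working it through.** **Lists side by side.** Carbamazepine, rifampin and rifabutin are in both. Phenobarbital is in both only if read as a long-acting barbiturate. Phenytoin, isoniazid, nevirapine, clarithromycin, erythromycin, indinavir and ritonavir are in 6.5.2 only.

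**Inputs from Section 10.2.** N = 80; means 231.7 and 291.7; SDs 94.0 and 101.8; two-sided alpha 0.05; unequal-variance t-test. The allocation ratio is not stated; 40 per arm is assumed.

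**The plan's own figure.** SE = √(94.0²/40 + 101.8²/40) = 21.91. Noncentrality = 60/21.91 = 2.74, with about 77.5 degrees of freedom. Power = 77.2%, which matches the stated 77%.

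**Adding users.** Suppose a fraction f of each arm has its level multiplied by k. For an arm with mean m and SD s:

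- new mean = m(1 − f + fk)
- new variance = (m² + s²)(1 − f + fk²) − (new mean)²

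Example with f = 0.05 and k = 0.5. Lower arm: mean 231.7 × 0.975 = 225.9; variance 62,520.9 × 0.9625 − 225.9075² = 9,142; SD 95.6. Higher arm: mean 284.4, SD 104.8. The difference is 58.5, SE 22.43, noncentrality 2.61, power 73.1%.

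| Assumed effect on level | Users per arm | Means | SDs | CVs | Power |
|---|---|---|---|---|---|
| none | 0% | 231.7 / 291.7 | 94.0 / 101.8 | 41% / 35% | 77% |
| 50% cut | 5% | 225.9 / 284.4 | 95.6 / 104.8 | 42% / 37% | 73% |
| 50% cut | 10% | 220.1 / 277.1 | 96.9 / 107.2 | 44% / 39% | 69% |
| 80% cut | 5% | 222.4 / 280.0 | 100.2 / 111.6 | 45% / 40% | 67% |
| 80% cut | 10% | 213.2 / 268.4 | 105.3 / 119.5 | 49% / 45% | 58% |
| 1.5-fold rise | 5% | 237.5 / 299.0 | 100.1 / 109.6 | 42% / 37% | 73% |
| 1.5-fold rise | 10% | 243.3 / 306.3 | 105.6 / 116.5 | 43% / 38% | 71% |

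**Chance imbalance.** Take five users in all and an 80% cut.

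- One user in the lower arm and four in the higher: 291.7 × 0.92 − 231.7 × 0.98 = 268.4 − 227.1 = 41.3.
- The mirror split: 291.7 × 0.98 − 231.7 × 0.92 = 285.9 − 213.2 = 72.7, with power about 86%.

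Each split has a probability of about 15% when five users are randomized 40/40. The planned difference of 60 can therefore shrink or widen.

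**What adjustment recovers.** In simulation with a 50% cut, adding baseline use as a covariate regained about 3 points of power at 5% use and about 6 points at 10% use (69% to 75%). When some users have lowered and some raised levels, a single combined indicator gains only about 1 point, so the two directions need separate indicators.

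**The case against.** - **The lists need not match.** Section 6.5.2 presents its drugs as examples, and an eligibility list and an interaction advisory can serve different purposes. This stands: a reader might infer a flat contradiction, and the text does not support one. The gap is the lack of a rule for the treatment period and for the analysis.
- **Safeguards exist.** Active TB is excluded (item 11), which removes one reason for antimycobacterial use. Randomization is stratified by HIV status, which helps balance antiretrovirals. Eligibility includes a medication review (Section 8.1). These stand and make serious imbalance less likely. They do not remove the added spread, and stratifying by HIV status does not balance individual drugs.
- **The sizes are assumed.** This also stands. HIV-positive patients are eligible, but the documents do not say how many will enrol or what they will take. The 80% cut has no source in the documents. Section 10.2 does not say whether its SDs already include patients on usual co-medication; if they do, the table counts some variability twice.
- **Permitting ordinary co-medication is a legitimate choice in a treatment trial.** Agreed. That choice still needs an analysis plan.
- **Exclusion 12 speaks of concurrent use, which could mean ongoing use.** Its 5-day window and assessment at baseline do not support that reading.
- **The Manual of Procedures may hold further rules.** It was not available for this review.

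**Conclusion.** The point holds in a limited form. Drugs that the protocol says alter itraconazole levels can be present at the primary Day 14 sample, and Section 10.1 makes no advance provision for them. With roughly balanced use, the consequence is added variability, higher CVs and some lost power: from 77% to between about 73% and 58% over the assumed range, and 73% to 69% if only the milder effects (a 50% cut or a 1.5-fold rise) are considered. These figures rest on assumed use in 5% to 10% of each arm, assumed effects, 40 patients per arm, and SDs in Section 10.2 that are free of interactions.

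A reader might also infer that the sample size calculation is wrong or that the comparison is biased against one arm. Neither follows. The stated power reproduces, and a chance imbalance can move the difference either way.

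**What to change.** 1. In Section 10.1, pre-specify two separate covariates in the linear model for Day 14 PK: use at baseline of a level-lowering drug named in 6.5.2, and use at baseline of a level-raising one. This replaces adjustment only after an imbalance has been observed.
2. Add a sensitivity analysis of Day 14 PK, including the CVs, without samples drawn while a listed drug is recorded. A baseline covariate cannot capture drugs started after Day 1, and this analysis can. Label it as sensitivity only, because it selects on an event after randomization in an open-label trial and can itself unbalance the arms.
3. The clinical team should reconcile exclusion 12 with Section 6.5.2 and state whether the restriction applies through the PK samples. Which drugs to restrict, and for how long, is their decision.

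The cost is at most two degrees of freedom, minor analysis work and some protocol wording. The drug records are already collected under Section 6.5.1. If the clinical team extends the restriction, slightly fewer patients may be eligible.
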